5.4.3 Hematopathology Section of the Laboratory of Pathology (Tissue samples)

Archival and/or freshly collected and processed tumor tissue may be stored in the Hematopathology Section of Laboratory of Pathology until ready for planned and/or future research assays if the patient has agreed to allowing specimens to be used in future research studies. IRB approval will be obtained before using any samples to conduct studies that are not described

within this protocol. Samples will be stored under conditions appropriate to the type of sample and processing (e.g., ambient or frozen).

Tissue that is given to the technician will be assigned an accession number (HP#) in the HP Case Logbook; sample tracking also takes place with a FileMaker Pro data base called HP Patient Information and Specimen Inventory. A Patient background sheet may be filled out and filed with any accompanying paperwork, with final reports and any supplemental reports that follow added as completed.

6 DATA COLLECTION AND EVALUATION

6.1 DATA COLLECTION

6.1.1 Summary

The PI will be responsible for overseeing entry of data into an in-house password protected electronic system (C3D) and ensuring data accuracy, consistency and timeliness. The principal investigator, associate investigators/research nurses and/or a contracted data manager will assist with the data management efforts. Primary and final analyzed data will have identifiers so that research data can be attributed to an individual human subject participant.

All adverse events (AEs), including clinically significant abnormal findings on laboratory evaluations, regardless of severity, will be followed until return to baseline or stabilization of event.

Document AEs from the first study intervention, Study Day 1, through 30 days after the last dose of study treatment. After 30 days, only adverse events which are serious and related to the study intervention need to be recorded.

End of study procedures: Data will be stored according to HHS, FDA regulations, and NIH Intramural Records Retention Schedule as applicable.

Loss or destruction of data: Should we become aware that a major breach in our plan to protect subject confidentiality and trial data has occurred, this will be reported expeditiously per requirements in section [7.2.1](#).

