laboratory abnormalities include early (treatment days 1-4) leukopenia, lymphopenia, thrombocytopenia, transaminitis, anemia, hypoalbuminemia during the whole treatment cycle, late cycle rises in bilirubin in patients treated with doses ≥ 2 mcg/kg and the dramatic spike in lymphocytes that occurs in the 72 hours after completion of the CIV infusion. The norm is for most of these laboratory abnormalities to begin returning or to resolve to baseline while treatment continues. There has been no evidence of increased risk of infection or requirement for antibiotic treatment during the period of cytopenias or increased bleeding during the period of decreased platelets. Decreases in hemoglobin (Hgb), which most likely is related to increased sequestration of red blood cells in the liver and spleen, generally require more time to return to pretreatment levels. This incidence of anemia has possibly been greater in the patients treated with the 5-day regimen and the 3, 4 or 5 mcg/kg dose levels, but this assessment has been complicated by the fact that 8 of the 10 patients treated in these dosing cohorts have GI malignancies and were found to be iron deficient. Some patients were transfused during their 2nd or later cycle of treatment and those who tolerated oral iron replacement therapy had replenishment of their iron stores to improve their Hgb level. A number of the patients previously treated in the rhIL-15 trials had past history of autoimmune phenomena related to their prior cancer treatment with checkpoint inhibitors and none of these patients developed new or recurrent autoimmune toxicities.

As seen in **Figure 4**, the rate and severity of irAEs is also generally lower for anti-PD-L1 agents [77], including avelumab (**Table 4**), with the onset of the clinical events of greatest concern occurring generally 2 to 3 months after initiation of treatment. Avelumab has been approved by the FDA for the treatment of metastatic refractory urothelial cancers, has a safety database that exceeds 2000 patients and has a very well characterized AE profile [57].

[figure not shown]

Figure 4: Distribution of irAEs for anti-PD-L1agents [77]

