3.6.1 Safety Follow-Up Visit

The safety follow-up visit should occur 30 days (± 7 days) after the last dose of trial treatment, or before the initiation of a new anti-cancer treatment, whichever comes first. Required testing is as noted in the Study Calendars (Section [APPENDIX F](#)). All AEs that occur prior to the Safety Follow-Up Visit should be recorded. Patients with an ongoing, treatment-related AE of Grade > 1 will be followed until the resolution of the AE to Grade 0-1, stabilization of the AE in the opinion of the investigator, or until the beginning of a new anti-neoplastic therapy, whichever occurs first. SAEs that occur within 30 days of the end of treatment or before initiation of a new anti-cancer treatment should also be followed and recorded.

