3.6.2 Extended Safety Follow-up

Given the potential risk for delayed immune-related toxicities, safety follow-up must be performed up to 90 (+14) days after the last dose of avelumab administration. This may be performed either via a clinic visit or via a telephone call/email with subsequent clinic visit requested in case any concerns are noted during the telephone call/email.

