10.2.1 Early stopping criteria

An early stopping criterion for toxicity for the whole trial itself would be if ≥ 2 of the first 9 or ≥ 4 of the first 17 patients has unacceptable toxicity or an irAE that required discontinuation of avelumab and/or initiation corticosteroid treatment.

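### Non-serious immune-related AEs first arising 31 to 90 days after last treatment need not be recorded, although the protocol requires safety follow-up over that period to look for them

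*Combined protocol and SAP*

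**What the plan says.** **Recording.** Section 6.1.1 sets the main window: "Document AEs from the first study intervention, Study Day 1, through 30 days after the last dose of study treatment". After that, "After 30 days, only adverse events which are serious and related to the study intervention need to be recorded". Section 8.2 sends the reader to Section 6.1 for the recording timeframe, so this text governs. Section 3.6.1 ties recording to the 30-day visit: "All AEs that occur prior to the Safety Follow-Up Visit should be recorded". Section 4.1 stops concomitant-medication recording 30 days after the last dose.

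**Follow-up.** Section 3.6.2 opens with "Given the potential risk for delayed immune-related toxicities" and then states that "safety follow-up must be performed up to 90 (+14) days after the last dose of avelumab administration". On the form of contact it adds: "This may be performed either via a clinic visit or via a telephone call/email". Footnote 2 of the study calendar (Appendix F) counts both the 30-day and the 90 (+14)-day contacts as safety follow-up. The calendar row for AE assessment and medication review appears to be marked in that column.

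**Use of the data.** Section 10.1.2 makes the rate and severity of AEs a secondary endpoint, with no time window. Section 10.2.1 stops the trial if at least 2 of the first 9 or 4 of the first 17 patients have unacceptable toxicity or "an irAE that required discontinuation of avelumab and/or initiation corticosteroid treatment". It requires neither seriousness nor a particular observation period.

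**Expected timing.** Section 1.3 describes irAEs "with the onset of the clinical events of greatest concern occurring generally 2 to 3 months after initiation of treatment", and expects them in this trial during cycle 2 or 3.

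**The concern.** The protocol arranges a contact specifically to find delayed immune toxicity, but does not require the non-serious findings to be entered. Take a non-serious irAE first treated with corticosteroids 45 days after the last dose. It fits the wording of the stopping rule, yet neither the event (Section 6.1.1) nor the steroid (Section 4.1) has to be in the database.

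Section 3.1 says that there is no earlier safety experience with this combination, so its AE profile is one of the main things the trial will report. If late non-serious irAEs are entered at one person's discretion and not another's, the reported rate depends on habit as well as on toxicity. Any loss would be uneven, because patients who stop early have the shortest full-recording window.

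**Working it through.** The plan states no figure for AE capture and no operating characteristics for the stopping rule, so there is nothing to reproduce. The check is calendar arithmetic, followed by an illustration.

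**Inputs.** Avelumab is given on days 8 and 22 of each 28-day cycle, for at most 4 cycles (Section 3.1). Full recording ends at +30 days (Section 6.1.1) and the extended contact falls at +90 days (Section 3.6.2). Table 4 median onsets are colitis 2.1 months, pneumonitis and adrenal 2.5, thyroid 2.8 and hepatitis 3.2. I assume no cycle delays, both avelumab doses given in the last cycle, and 30.44 days per month.

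**Windows.** The last avelumab day after c cycles is 28(c − 1) + 22. Add 30 or 90 for the end of each window. Subtract 8 to count from first avelumab.

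| Cycles | Last avelumab (study day) | +30: study day (from first avelumab) | +90: study day (from first avelumab) |
|---|---|---|---|
| 1 | 22 | 52 (44) | 112 (104) |
| 2 | 50 | 80 (72) | 140 (132) |
| 3 | 78 | 108 (100) | 168 (160) |
| 4 | 106 | 136 (128) | 196 (188) |

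For every patient the unrecorded stretch is 90 − 30 = 60 days, or 74 with the +14 allowance.

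**Medians in days.** 2.1 × 30.44 = 64; 2.5 × 30.44 = 76; 2.8 × 30.44 = 85; 3.2 × 30.44 = 97.

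**Comparison, from first avelumab.**
- 1 cycle (44 days): every median is outside.
- 2 cycles (72 days): colitis is inside; pneumonitis, adrenal, thyroid and hepatitis are outside.
- 3 cycles (100 days): all are inside, hepatitis by about 3 days.
- 4 cycles (128 days): all are inside.

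Counted from study day 1, the 2-cycle window is 80 days and only thyroid and hepatitis are outside; the other rows do not change. With a 90-day window every median is inside whatever the number of cycles. The upper ends of the Table 4 ranges (8 to 15 months) are outside both windows.

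**Stopping rule, illustration only.** Let p be the true rate of qualifying events and m the fraction not counted. With q = p(1 − m), X9 the count in the first 9 patients and X17 the count in the first 17,

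P(cross) = P(X9 ≥ 2 or X17 ≥ 4) = 1 − Σ(x = 0 to 1) Σ(y = 0 to 3 − x) Bin(x; 9, q) · Bin(y; 8, q).

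| p | m = 0 | m = 10% | m = 25% | m = 50% |
|---|---|---|---|---|
| 10% | 0.24 | 0.20 | 0.15 | 0.07 |
| 14.2% | 0.41 | 0.35 | 0.27 | 0.14 |
| 20% | 0.63 | 0.56 | 0.44 | 0.24 |

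The 14.2% is the any-grade irAE rate for single-agent avelumab in Table 2, used as a high reference because many such events need no corticosteroid. All values of m, and the 10% and 20% rates, are assumptions.

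**The case against.** Several points against the concern stand.

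- **A minimum, not a ban.** A reader might infer that Section 6.1.1 tells staff not to record late events. It says only what has to be recorded. The problem is optional and therefore uneven capture.
- **Onset is counted from the start of treatment.** A reader might take the 2-to-3-month onset as proof that irAEs are systematically lost. For patients given 3 or 4 cycles every Table 4 median falls inside full recording, and Section 1.3 expects these events on treatment.
- **The size of the loss cannot be derived.** It is tempting to say that more than half of the events in early stoppers would go unrecorded. Table 4 comes from the avelumab safety database, possibly with longer exposure, and nothing shows that its medians apply after one or two cycles.
- **Most of the stopping rule is untouched.** An irAE that forces avelumab to be discontinued arises while avelumab is still being given, so that limb is unaffected. Thyroid events are handled in Table 15 with hormone or anti-thyroid treatment and would not normally reach the corticosteroid limb. Section 8.1.2 lets important medical events be classed as serious, so some steroid-treated irAEs stay captured. Section 10.2.1 does not tie the rule to CRF entries, and under Section 7.3.1 the principal investigator reviews each patient's AE data.
- **Small numbers.** Non-thyroid irAEs with a listed median total 1.2 + 0.9 + 1.5 + 0.5 = 4.1%. At the 25-patient ceiling that is 0.041 × 25 ≈ 1 event at any time, at single-agent rates. The documents give no rate for the combination.

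These points limit the concern but leave the mismatch in place. Scheduling an AE assessment at 90 days is not the same as requiring its findings to be entered, and Section 3.6.1 extends follow-up only for AEs already ongoing.

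**Conclusion.** The concern holds in limited form. Between 31 and 90 days after last treatment, a non-serious irAE and the corticosteroid started for it need not be recorded, although the protocol mandates follow-up for such events over that period. The AE endpoint and the corticosteroid limb of the stopping rule may therefore be under-counted. Exposure is greatest for patients who stop after 1 or 2 cycles. That is a foreseeable group, since entry requires progression after at least two prior therapies and the first restaging follows cycle 2. Late-onset events are exposed after any number of cycles.

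The documents support the direction and location of the gap but not a missed fraction. They do not support a claim that the rule as a whole is compromised or that serious related toxicity is lost. The comparison with the medians rests on Table 4 onset times applying here, on the schedule running without delay, and on both avelumab doses being given in the last cycle. The correction is worth making because the gap is specific and cheap to close.

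**What to change.** - **Section 6.1.1:** record all irAEs of any grade, and any AE leading to corticosteroids, through the 90 (+14)-day contact. Keep the serious-and-related limit for other AEs after day 30.
- **Section 4.1:** extend recording over the same period to corticosteroids and other immunosuppressants started for irAEs. Otherwise the treatment that triggers the stopping rule would still not have to be documented.
- **Section 3.6.1:** align its recording sentence with the new window.
- **Sections 10.1.2 and 10.2.1:** state this observation window for the AE endpoint and for the stopping rule.

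The cost is a few more CRF entries at a contact already required, and possibly slightly less favourable AE rates. Events beyond 90 (+14) days would remain limited to serious and related ones, and the report should say so. Only data capture changes; no treatment rule does.

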6.1.2 Data Collection/Reporting Exceptions

6.1.2.1 Abnormal Laboratory Values

An abnormal laboratory value will be considered an AE **only** if the laboratory abnormality is characterized by any of the following:

- Results in discontinuation from the study
- Is associated with clinical signs or symptoms
- Requires treatment or any other therapeutic intervention
- Is associated with death or another serious adverse event, including hospitalization
- Is judged by the Investigator to be of significant clinical impact
- If any abnormal laboratory result is considered clinically significant, the investigator will provide details about the action taken with respect to the test drug and about the patient's outcome.

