Distribution of (A) grade 1 to 2 and (B) grade 3 to 5 immune-related adverse events (irAEs) for all tumor types in the main clinical trials with anti-cytotoxic T-cell lymphocyte-4 (anti-CTLA-4), anti-programmed death 1 (PD-1), or anti-PD ligand 1 (PD-L1) antibodies as single therapies. The values quoted are the median (range) irAE rates for the set of clinical trials as a whole.

Table 4: Summary of irAEs in Avelumab Safety Database

irAE	Overall rate %	Grade 3 through 5%	Onset of Symptoms	
			Median	Range
Pneumonitis	1.2	0.5	2.5 months	3 days – 11 months
Hepatitis	0.9	0.5 (grade 3 only)	3.2 months	7 days -15 months
Colitis	1.5	0.4 (grade 3 only)	2.1 months	2 days – 11 months
Adrenal	0.5	0.1 (grade 3 only)	2.5 months	1 day – 8 months
Thyroid	6	0.2 (grade 3 only)	2.8 months	14 days – 13 months
Diabetes	0.1	0.1 (grade 3 only)	NA	NA
Nephritis	0.1	NA	NA	NA

Infusion reaction initially occurred in one quarter of the patients receiving avelumab including 9 patients with grade 3 (0.5%) and 3 patients with grade 4 (0.2%) events that were successfully controlled with antihistamines and IV corticosteroids. The avelumab package insert now recommends routine premedication with an antihistamine during the first 4 infusions. Anti-PD-1 (nivolumab, pembrolizumab or PDR001) antibodies have been given in combination with all versions of rhIL-15, E. coli (NCI produced) single chain agent, heterodimeric IL-15 (Novartis) and the ALT-803 superagonist (Altor now NantKWest). While the number of patients treated with these combinations is still modest, there has not been a new safety signal or evidence of synergistic toxicities. Given the close temporal relationship of CIV rhIL-15 treatment to the transient grade 3 hematologic and occasional metabolic abnormalities, we anticipate that these events will not complicate the recognition of the rare autoimmune events seen with avelumab which would normally become apparent during the second or third cycle of treatment. We believe it is reasonable to use our standard DLT exclusion algorithm even in the initial dose level safety evaluation of patients and will view sustained or delayed grade 3 elevations of liver function tests (LFTs) as DLTs.

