3.1.1 Dose-Limiting Toxicity

A dose-limiting toxicity (DLT) is defined as: any grade 3, 4, or 5 toxicity if not incontrovertibly due to disease progression or an extraneous cause, and deemed possibly, probably or definitely related to IL-15 or avelumab by the PI or designee during the first 28 days of treatment, only for the Safety Run-in cohort (Cohort 1) with the following exceptions.:

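### The laboratory AE rule has no grade, DLT or dose-change trigger, so grade 3 or higher laboratory toxicity can be left out of the AE summary unless the investigator chooses to enter it

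*Combined protocol and SAP*

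**What the plan says.** Section 6.1.2.1 limits which laboratory results count. It sets out when "An abnormal laboratory value will be considered an AE", and one of five conditions must be met:

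- Leaving the study: "Results in discontinuation from the study"
- Clinical picture: the patient has accompanying signs or symptoms.
- Need for therapy: "Requires treatment or any other therapeutic intervention"
- Outcome: there is a link to a death or a further SAE.
- Discretion: "Is judged by the Investigator to be of significant clinical impact"

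A sixth bullet asks for details when a result is considered clinically significant. It is a documentation instruction, not a further condition.

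Section 3.1.1 works by grade. A DLT is "any grade 3, 4, or 5 toxicity if not incontrovertibly due to disease progression or an extraneous cause", at least possibly related to either drug, in the first 28 days, in the Safety Run-in cohort only. Sections 3.1.1.1 and 3.1.1.2 except several laboratory changes. Section 1.3 adds that the investigators "will view sustained or delayed grade 3 elevations of liver function tests (LFTs) as DLTs".

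Section 3.3.1 allows rhIL-15 to be interrupted and reduced in Cohort 2 for reversible grade 3 thrombocytopenia or liver-test abnormalities, among other events. Section 8.1.1 defines an AE broadly and includes abnormal laboratory findings without the Section 6.1.2.1 limit. Sections 10.1.2 and 10.4.2 make the rate and severity of AEs, by grade and type, a secondary endpoint.

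**The concern.** The rule that decides what enters the AE data and the rules that decide what is dose-limiting or dose-changing use different criteria, and nothing in the protocol links them. No sentence says that every DLT, or every laboratory value that alters dosing, is recorded as an AE.

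This matters because much of the expected toxicity of rhIL-15 is found in the laboratory. Section 1.3 lists cytopenias, transaminitis, hypoalbuminemia and late bilirubin rises as common. Section 1.2.10.1 reports that two of four patients at 1.0 mcg/kg/day by bolus had asymptomatic grade 3 ALT and AST elevations that were dose-limiting, and that a grade 3 thrombocytopenia was one of two events that led to lower dose levels being added. Section 1.2.10.2 lists hepatotoxicity as one of two DLTs at 4.0 mcg/kg/day on the 10-day infusion. According to Section 3.1, the combination with avelumab has no prior safety experience, so the graded AE table will be the main published description of its tolerability.

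**Working it through.** The plan gives no figure on this point, so the check runs specific events through both sets of rules.

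**Inputs.** AE conditions: Section 6.1.2.1. DLT definition and exceptions: Sections 3.1.1 to 3.1.1.2. Dose changes: Section 3.3.1. Stopping therapy versus leaving the study: Sections 3.9.1 and 3.9.2. Denominators: Sections 10.2 and 10.3.1.

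**Step 1: does a DLT trigger the discontinuation condition?** Section 3.9.1 lists Section 3.1.1 toxicity as a reason to stop protocol therapy. Section 3.9.2 lists the reasons for leaving the study: subject request, loss to follow-up, death and study cancellation. Toxicity is not one of them. The Section 6.1.2.1 condition refers to the study, so read literally a DLT that ends treatment does not meet it.

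**Step 2: which laboratory events remain DLTs after the exceptions?** Lymphocytopenia and neutropenia without infection, grade 3 leukocytosis, and grade 3 electrolyte or albumin changes that last under 24 hours and respond to intervention are excepted. So are grade 3 liver tests lasting under 7 days that are not attributed to avelumab and come without clinical hepatic dysfunction. Thrombocytopenia, anemia, lipase, amylase and CPK are not on the exception lists, and liver-test rises of longer duration are not excepted.

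**Step 3: four events, each related, asymptomatic and untreated.**

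| Event | Status under Section 3 | AE condition met automatically |
|---|---|---|
| Run-in, grade 3 thrombocytopenia | DLT (3.1.1) | None |
| Run-in, grade 3 transaminase rise beyond 7 days, not managed as an irAE | DLT (3.1.1, 1.3) | None |
| Cohort 2, grade 3 platelets or liver tests with rhIL-15 interrupted or reduced | Dose change (3.3.1) | None |
| Grade 3 or 4 lymphocytopenia without infection | Excepted, drugs continue (3.1.1.1) | None |

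In all four, the only remaining route into the AE data is the investigator's judgement of clinical impact. The first three change or end treatment. The fourth can be absent from both the DLT count and the AE table. The inpatient stay in cycle 1 does not help, because Section 8.1.2 does not count a protocol-required admission as serious when there is no serious deterioration.

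**Step 4: size per missed patient.** With n patients in the safety summary, one unrecorded patient lowers the reported rate of that event by 1/n. Section 10.2 gives a minimum enrolment of 12 and a maximum of 25.

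- n = 25: 1/25 = 4.0 percentage points
- n = 12: 1/12 = 8.3 percentage points

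The documents do not give the frequency of asymptomatic, untreated, grade 3 or higher laboratory values on the 5-day schedule, so the expected number missed cannot be calculated.

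**The case against.** The strongest reply is that the gap is narrow in practice.

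- **Liver tests.** Table 12 lists prednisone for grade 3 to 4 hepatic irAEs, which meets the treatment condition. This stands for rises managed as immune-related. It does not cover a rise attributed to rhIL-15, which is infused on days 1 to 5, before the first avelumab dose on day 8.
- **Other treated events.** Electrolyte supplementation (3.1.1.2) and albumin or red-cell transfusion (3.2.5) also meet the treatment condition. This stands, so it would be wrong to say that laboratory toxicity as a class disappears from the summary.
- **Discontinuation.** If the wording about the study is meant to include protocol therapy, every DLT that ends treatment becomes an AE. Section 3.3.3 even calls the Section 3.1.1 events adverse events, which suggests that intent. The text does not say so, and dose interruption or reduction would still be uncovered.
- **Judgement.** An investigator who calls a value dose-limiting would probably also judge it of significant clinical impact. That is likely, but discretionary.
- **Scope.** DLTs apply only to the run-in's first 28 days, and the exceptions remove many of the expected asymptomatic changes. Section 1.2.10.2 reports ten patients on the 5-day schedule at 3 to 5 mcg/kg/day without a DLT. This limits how often the DLT part of the gap would arise.

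A reader might go further and infer that DLTs would go uncounted, so that a toxic dose level is cleared too easily or the Section 10.2.1 rule fails to act. The documents do not support that. Section 3.1.1 rests on a toxicity judged by the PI or designee, not on an AE entry. Section 7.3.1 bases dose decisions on toxicity data discussed at weekly meetings. Section 3.5 requires all test results to be reviewed before each cycle. The Section 10.2.1 rule counts unacceptable toxicity or irAEs that led to avelumab discontinuation or corticosteroids, much of which can be traced from treatment records. For that reason no change in the run-in's operating characteristics is calculated here.

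**Conclusion.** The gap is real but limited to recording. As written, Section 6.1.2.1 allows an asymptomatic, untreated laboratory value that is a DLT in the run-in, or that changes dosing in Cohort 2, to stay out of the AE data unless the investigator enters it. Sections 6.1.2.1 and 8.1.1 also give two different scopes for a laboratory AE.

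The demonstrated consequence is that the secondary endpoint, rate and severity of AEs by grade and type, can be incomplete, by 4.0 to 8.3 percentage points per missed patient depending on final enrolment. The conclusion rests on a literal reading of the discontinuation condition, and on some such values being neither treated nor judged of significant clinical impact. Dose escalation, the stopping rule and the response endpoint are not shown to be affected. It should be corrected because the correction is simple and the affected events belong to the drug's known toxicity profile.

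**What to change.** 1. Add to Section 6.1.2.1 that any laboratory value meeting a DLT criterion in Section 3.1.1, or leading to interruption, reduction or discontinuation of either study drug under Section 3.3 or 3.9.1, is graded by CTCAE and recorded as an AE regardless of symptoms or treatment.
2. Reconcile Section 6.1.2.1 with Section 8.1.1 so that one definition of a laboratory AE applies, and state whether the discontinuation condition means protocol therapy, the study, or both.
3. Add to Section 10.4.2 a table of worst CTCAE grade per patient for all scheduled laboratory tests, derived from the laboratory data. Excepted grade 3 to 4 changes then appear in the safety summary without each needing an AE entry.

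The tests are already scheduled in Appendix F, and no dose, DLT criterion or clinical rule changes. The cost is more AE rows, one extra table and less favourable reported rates.
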